13.6.4. Safety

Adverse Events		
Adverse Events of Special Interest (AESI)		
AESI will be defined per the version of the PSAP/MedDRA in effect at the time of DBR.		
Malignant Neoplasms		
• Malignancies Excluding non-melanoma skin cancer (NMSC)		
Malignancies Including NMSC		
Solid Tumour		
Hematologic		
• Skin (All)		
NMSC		
 Excluding NMSC 		
 Tumours of unspecified malignancy adjudicated as malignant per GSK 		
Post-Infusion Systemic Reactions (PISR)		

- PISR per Anaphylactic Reaction Customized MedDRA Query (CMQ) narrow search
- PISR per Anaphylactic Reaction CMQ broad search
- PISR per Anaphylactic Reaction CMQ algorithmic search
- Serious Anaphylaxis per Sampson Criteria per GSK adjudication
- Serious Acute PISR/Hypersensitivity Per GSK adjudication
 - Serious Acute PISR Excluding Hypersensitivity per GSK adjudication

Adverse Events
Adverse Events Advers
Serious Acute Hypersensitivity Reactions per GSK adjudication
Serious Delayed Acute Hypersensitivity Reactions per GSK adjudication
Serious Delayed Non-Acute Hypersensitivity Reactions per GSK adjudication
All Infections of Special Interest (Opportunistic Infections (OI), Herpes Zoster (HZ), Tuberculosis
(TB), And Sepsis; All and Serious, separately)
All opportunistic infections (OI) per GSK adjudication
OI per GSK adjudication excluding Tuberculosis and Herpes Zoster
Active Tuberculosis
Non-Opportunistic
Opportunistic
Herpes Zoster
Non-Opportunistic
Opportunistic
 Recurrent
 Disseminated
Sepsis
Depression (including mood disorders and anxiety)/suicide/self-injury (All and Serious, separately)
Depression (including mood disorders and anxiety) (excluding suicide and self-injury)
Suicide/self-injury
Serous suicide/self-injury per GSK adjudication
Suicidal Behaviour
 Completed Suicide
Suicidal Ideation
 Self-injurious Behaviour without Suicidal Intent
Deaths

Laboratory Parameters

- If a laboratory value which is expected to have a numeric value for summary purposes, has a non-detectable level reported in the database, where the numeric value is missing, but typically a character value starting with '<x' or '>x' (or indicated as less than x or greater than x in the comment field) is present, the number of significant digits in the observed values will be used to determine how much to add or subtract in order to impute the corresponding numeric value.
 - Example 1: 2 Significant Digits = '< x ' becomes x 0.01
 - Example 2: 1 Significant Digit = '> x' becomes x + 0.1
- Example 3: 0 Significant Digits = '< x' becomes x 1

13.6.5. Pharmacokinetic

Belimumab concentration

• Assign zero to NQ values (Refer to GUI_51487 for further details)

13.6.6. Biomarker

13.6.6.1. Autoantibody, Complement, Immunoglobulins, and BLyS Protein

Bic	Biomarker Categorical Definitions		
Ant	i-ds DNA		
•	Positive: ≥ 30 IU /mL		
•	Negative: < 30 IU /mL		
AN	ANA		
•	Positive: index ≥ 0.80		
•	Negative: index < 0.80		
aC	aCL status		
•	Positive: if any of the three isotypes IgG, IgA or IgM are above the lower limit of quantification Negative: if at least one isotype is non-missing and none of the isotypes are above the lower limit of quantification Missing: if all three isotypes are missing		
BLyS Protein			
•	Below LOQ: <0.02048 ng/mL		
•	Above LOQ: ≥0.02048 ng/mL		
C3			
•	Positive: < 90 mg/dL		
•	Negative: ≥ 90 mg/dL		
•	Low: < 90 mg/dL		
•	High: > 180 mg/dL		
C4			
•	Positive: < 10 mg/dL		
•	Negative: ≥ 10 mg/dL		
•	Low: < 10 mg/dL		
•	High: > 40 mg/dL		
Imr	nunoglobulin G		
•	Low: $< 6.94 \text{ g/L}$		
• Imr	Normal/High: ≥ 6.94 g/L nunoglobulin A		
	•		
•	Low: $< 0.81 \text{ g/L}$		
• Imr	Normal/High: ≥ 0.81 g/L nunoglobulin M		
•	Low: $< 0.48 \text{ g/L}$		
•	Normal/high: ≥ 0.48 g/L		

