2.3. Study Design

Overview of Study Design ar	Overview of Study Design and Key Features	
	this long-term safety data to regulatory authorities in the initial BLA and other marketing authorization submissions). Additional interim analyses may be required to support subsequent safety updates to regulatory authorities. No interim analyses were conducted.	
Sample Size	• The total target sample size was 71 subjects and 80 were enrolled. The target sample size for subjects in the treatment holiday and control groups was 10 (12 enrolled) and 26 (29 enrolled) subjects respectively. A target sample size of 35 (39 enrolled) subjects in the long-term discontinuation group was anticipated.	

Note: Subjects from China participated in BEL113750 OL phase rather than in BEL114333, and were therefore eligible to enter BEL116027 from BEL113750 OL, per a China country-specific protocol amendment 01.

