6.2. Baseline Disease Activity and Other Baseline Endpoints

A summary of baseline disease activity will be provided, including counts and percentages for categorical endpoints and descriptive statistics for the continuous endpoints and scores.

Table 3 provides indicators of baseline disease activity that will be summarized. Some of these parameters will be summarized on the by visit summary for that parameter according to the table specifications.

Endpoint	Categories & Summaries at Baseline
SELENA-SLEDAI category	Continuous
	Categorical
	• 0, 1, 2, 3
SELENA SLEDAI by organ domain	Categorical
and item at baseline	Presented if Yes
Complement & BLyS Levels	Complement C3 and C4 (mg/dL)
	Continuous
	Categorical
	Positive, Negative
	Low, Normal, High
	(See Section 13.6.6 for definitions)
	BLyS Protein [ng/mL]
	Continuous
	Categorical
	 Below LLOQ: <0.061 ng/mL for China samples and <0.02048 ng/mL for all others
SLE Flare Index	Categorical
	At least 1 flare, At least 1 severe flare
PGA	Continuous
	Categorical
	• 0-1, >1 – 2.5, > 2.5
SLICC/ACR Damage Index	Continuous
	Categorical
	• 0, 1, > 1

Table 3 Baseline Disease Activity Endpoints

2018N381035_00 BEL116027

Endpoint	Categories & Summaries at Baseline
Proteinuria (based on spot urine using protein: creatinine mg/mg ratio)	Continuous Categorical (units are g/24hr equivalent) • $\leq 0.5, > 0.5$ • Subcategories of > 0.5 • $>0.5 - < 1$ • $1 - < 2$ • ≥ 2
B cells: CD19+ CD20+ CD20+/27+ memory CD20+/27- naïve CD20+/69+ activated CD20+/138+ plasmacytoid CD19+/27 ^{BRIGHT} /38 ^{BRIGHT} SLE subset CD20-/138+ plasma	Continuous
Autoantibody Levels	Anti-dsDNA [IU/mL] Continuous Categorical Positive: >=30 IU/mL Negative: <30 IU/mL ANA [Titer] Continuous Categorical Positive: Index >=0.80 Negative: Index <0.80 aCL Status Categorical Positive, Negative, Missing (See Section 13.6.6 for definitions)
anti-dsDNA and/or ANA positive	Categorical • Yes, No
Immunoglobulin Levels (IgG, IgA, and IgM [g/L])	Continuous Categorical IgG • Low: < 6.94 g/L, High: > 16.18 g/L IgM Low: < 0.48 g/L, High: > 2.71 g/L IgA • Low: < 0.81 g/L, High: > 4.63 g/L

Endpoint	Categories & Summaries at Baseline		

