13.7.2. Handling of Missing Data

Element	Reporting Detail
General	 Missing data occurs when any requested data is not provided, leading to blank fields on the collection instrument: These data will be indicated by the use of a "blank" in subject listing displays. Unless all data for a specific visit are missing in which case the data is excluded from the table. Answers such as "Not applicable" and "Not evaluable" are not considered to be missing data and should be displayed as such.
Outliers	• Any participants excluded from the summaries and/or statistical analyses will be documented along with the reason for exclusion in the clinical study report.
LOCF	 In the LOCF dataset, missing values will be carried forward from the previous, non-missing available on-treatment assessment. For the TH group, LOCF will not be applied across the TH and RS phases.
SLICC/ACR Damage Index	 Missing data due to prohibited medication or study withdrawal will be imputed using LOCF For the TH group, LOCF will not be applied across the TH and RS phases.
SELENA SLEDAI,	 Missing data will be imputed using LOCF. For the TH group, LOCF will not be applied across the TH and RS phases.

Element	Reporting Detail
Rebound, PGA	 If an individual SELENA SLEDAI item data is missing at the first timepoint in the RS phase, the item will be considered not present.
Reduction in Daily Prednisone Dose	 The Dropout (DO)/Prohibited Medication (PM)=Non-responder (NR) imputation will be applied. If a subject withdraws from the study and/or receives a protocol-prohibited medication prior to a scheduled visit, the subject will be considered a non-responder (i.e. no reduction in prednisone) for that and subsequent visits.
Average daily prednisone dose	Observed data will be used with no imputation.
Auto-antibodies, immunoglobulins, biomarkers, BLyS protein	Observed data will be used with no imputation
Immunogenicity	Observed data will be used with no imputation.

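### SAP 13.6.6.1 omits the China-specific BLyS limit given in Table 3, so a China value from 0.02048 to below 0.061 ng/mL falls in opposite categories in the two places

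*SAP*

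**What the plan says.** SAP 13.6.6.1, the section of categorical definitions for biomarkers, splits BLyS protein at a single value: "Below LOQ: <0.02048 ng/mL" and "Above LOQ: ≥0.02048 ng/mL". It makes no exception for any country or laboratory.

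SAP 6.2, Table 3, specifies the baseline disease activity summary. In the row for complement and BLyS, it gives the below-limit category for BLyS as "<0.061 ng/mL for China samples and <0.02048 ng/mL for all others". The same row carries the pointer "See Section 13.6.6 for definitions", which leads to the section holding the single cut.

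China subjects are in the trial: "Subjects from China participated in BEL113750 OL phase rather than in BEL114333" (SAP 2.3). The SAP's list of changes from the protocol (section 2.1) does not mention the two limits.

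**The concern.** The section that defines the category and the table that uses it disagree on the threshold for one country's samples. Two programmers working from the same SAP could produce different below-limit counts, each with a section to cite. Table 1.14, the display that Table 3 specifies, is marked for the headline results package, so the discrepancy would surface early. If 13.6.6.1 were followed, a China sample that the assay could not quantify might be reported as quantifiable.

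**Working it through.** **Inputs.** Single cut: 0.02048 ng/mL (SAP 13.6.6.1). China limit: 0.061 ng/mL; limit for all others: 0.02048 ng/mL (SAP Table 3).

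**Where the definitions disagree.** For non-China samples they agree. For China samples they disagree on values from 0.02048 to below 0.061 ng/mL.

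- Ratio of limits: 0.061 / 0.02048 = 2.98.
- Share of the width of the China sub-limit range (0 to 0.061) that lies in the disputed band: (0.061 − 0.02048) / 0.061 = 0.04052 / 0.061 = 66%. This is a share of the scale, not of samples.

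**What happens to a result reported as <0.061.** The outcome depends on the number stored. SAP 13.6.4 has a rule for laboratory results reported as less than x: "the number of significant digits in the observed values will be used to determine how much to add or subtract in order to impute the" missing number. Its worked examples stop at two digits, so its application to 0.061 can be read in two ways: by decimal places, 0.061 − 0.001 = 0.060; by significant digits, 0.061 − 0.01 = 0.051. The other substitutions in the table are assumptions, included to show the range.

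| Stored value for a China result <0.061 | Value (ng/mL) | By 13.6.6.1 | By Table 3 |
|---|---|---|---|
| 13.6.4 rule, decimal places | 0.060 | Above | Below |
| 13.6.4 rule, significant digits | 0.051 | Above | Below |
| Limit/√2 (assumed) | 0.043 | Above | Below |
| Limit/2 (assumed) | 0.0305 | Above | Below |
| Zero (assumed) | 0 | Below | Below |

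A raw instrument reading under 0.02048 would also be below the limit in both places.

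**Non-China check.** A result of <0.02048 becomes 0.02047 (decimal places) or 0.02038 (significant digits). Both are below the limit in both places, so the conflict is confined to China samples.

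**Where the category is used.** Table 3 calls for it at baseline. For BLyS, SAP 5.3.1 takes baseline from Day 0 of the parent study, before study treatment. SAP 6.2 adds that some parameters will be summarised by visit instead, without saying which. The listed BLyS outputs (Tables 5.22 and 5.23, Figure 5.7) show change or percent change, and the shift analyses in SAP 11.1.2.2 do not name BLyS.

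**The case against.** The best answer is that this is a wording mismatch with no practical effect. Table 3 is the only place that clearly asks for the category, and it prints the China limit beside BLyS. Its pointer to 13.6.6 follows the complement categories and comes before the BLyS entry, so it may not be meant for BLyS at all. A programmer working from Table 3 would classify China samples by the China limit. This stands as a reason to expect little harm. It does not settle the text, because 13.6.6.1 defines the BLyS category explicitly and without the exception.

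It can also be said that the rule in 13.6.4 does not reach BLyS. It sits under safety laboratory parameters, while for BLyS SAP 13.7.2 says "Observed data will be used with no imputation", and SAP 11.1.4 takes the same line for all biomarkers. Against that, SAP 13.8.1 lists BLyS protein among the laboratory parameters collected, and the no-imputation statement is a missing-data rule that does not say what number represents a below-limit result. The SAP leaves the matter open, so the 13.6.4 rule can serve only as one possible case.

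**Conclusion.** The conflict is real and unreconciled, and its consequence is minor. It affects a descriptive category of an exploratory biomarker, in Table 1.14 and in any by-visit summary that reuses the category. It can change the class only of China samples whose stored value lies from 0.02048 to below 0.061 ng/mL. The documents give neither the number of such samples nor the form in which China results are reported; the number could be zero. The conclusion assumes that Table 3 states the limits of the assays used, which the sponsor's laboratory can confirm. No primary or secondary efficacy result depends on it.

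A reader might infer two stronger conclusions that the documents do not support:

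- **That every unquantifiable China sample will be labelled quantifiable.** That follows only if such results are stored as a number of at least 0.02048. Zero, or a raw reading under 0.02048, is classified correctly under either definition, and the SAP does not say which applies.
- **That the misclassification will create an apparent difference between groups or regions after belimumab is stopped.** In this study BLyS is measured in the treatment holiday and long-term discontinuation groups only, and their countries of recruitment differ, so the idea is understandable. But the baseline category describes parent-study samples taken before treatment, the listed post-baseline BLyS displays do not use the category, and none is by region.

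**What to change.** In SAP 13.6.6.1, replace the single BLyS cut with the assay-specific limits in Table 3: 0.061 ng/mL for China samples and 0.02048 ng/mL for all others. Add that a result reported as below its assay's limit is classed as below LOQ directly, whatever number is stored for it; this removes the dependence on storage. If the laboratory confirms that a single limit applied throughout, state that limit in both places instead.

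The cost is one or two lines of SAP text and a check of the program for Table 1.14. No new data are needed, and nothing in the BLyS change or percent-change displays has to be altered on account of this point.

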13.6.6.2. B-cell Subsets

Flow Assays

B-cells can be assayed using 3 different flow panels (identification of the flow panel responsible for each record is stored in BIMETHCD in the data transfer): Not all assays

will have the full list of B-cells assessed, but data relating to CD19 B-cells are collected using all 3 assay methods, i.e. concentration of CD19 cells from the TBNK panel and CD19 event counts on the Plasma and Transitional panels (see detail in the table below).

Because the numbers of cells observed for the rare B-cell subsets are small, the concentration data cannot be adequately summarised in the units provided in the SI/SDTM data. Therefore, these subsets are normalized and converted to an appropriate unit of measurement, i.e. count/mL. To normalize a rare B-cell subset and convert to count/mL, the CD19+ B-cell event count from the same flow panel as the B-cell subset being converted is used in the derivation. For example, the CD19+ event count from the plasma flow panel is used to normalize B-cell subsets found in the plasma panel, whereas the CD19+ event count from the transitional panel is used when converting rare B-cell subsets from the transitional panel. The study RAP should detail which rare B-cell subsets will be normalized and converted.

Source data

Flow Panel	Biomarker testing method code	Biomarker category code (BICATCD) ¹	Analyte name	Biomarker test code (BITESTCD)	Units of Measurement (BIORRESU)
TBNK	FLWTBNK	CD19	CD19+	CONC	GI/L
TBNK	FLWTBNK	CD19	CD19+	%LYMPH	%
PLASMA	FLWPLSM	CD19	CD19+	EVENTS	EVENTS
TRANSITIONAL	FLWTRANS	CD19	CD19+	EVENTS	EVENTS
PLASMA	FLWPLSM	CD20	CD20+	CONC	GI/L
PLASMA	FLWPLSM	CD20	CD20+	%CD19+	%
PLASMA	FLWPLSM	CD20	CD20+	EVENTS	EVENTS
PLASMA	FLWPLSM	CDX136	Naïve CD20+ CD27-	CONC	GI/L
PLASMA	FLWPLSM	CDX136	Naïve CD20+ CD27-	%CD19+	%
PLASMA	FLWPLSM	CDX136	Naïve CD20+ CD27-	EVENTS	EVENTS
PLASMA	FLWPLSM	CDX137	Memory CD20+ CD27+	CONC	GI/L
PLASMA	FLWPLSM	CDX137	Memory CD20+ CD27+	%CD19+	%
PLASMA	FLWPLSM	CDX137	Memory CD20+ CD27+	EVENTS	EVENTS
PLASMA	FLWPLSM	CDX141	Activated CD20+ CD69+	CONC	GI/L
PLASMA	FLWPLSM	CDX141	Activated CD20+ CD69+	%CD19+	%
PLASMA	FLWPLSM	CDX143	Plasma CD20- CD138+	CONC	GI/L
PLASMA	FLWPLSM	CDX143	Plasma CD20- CD138+	%CD19+	%
PLASMA	FLWPLSM	CDX143	Plasma CD20- CD138+	EVENTS	EVENTS
PLASMA	FLWPLSM	CDX145	Plasmacytoid CD20+ CD138+	CONC	GI/L
PLASMA	FLWPLSM	CDX145	Plasmacytoid CD20+ CD138+	%CD19+	%
PLASMA	FLWPLSM	CDX145	Plasmacytoid CD20+ CD138+	EVENTS	EVENTS
PLASMA	FLWPLSM	CDX156	SLE Subset CD27+CD38+CD19+	CONC	GI/L
PLASMA	FLWPLSM	CDX156	SLE Subset CD27+CD38+CD19+	%CD19+	%
PLASMA	FLWPLSM	CDX156	SLE Subset CD27+CD38+CD19+	EVENTS	EVENTS
			BICATCD=CDX141 for its concentration Il subsets, the BICATCD is the same		

Below are the important variables included in a source data transfer for the B-cells to be reported in this study.

B-cell unit conversions and Normalization of Rare B-cell Subsets

The Benlysta program standard is to report common B-cells (CD19, CD20, naïve, and memory) in counts per microliter (uL). Common B-cells are not normalized but they must be converted to uL for reporting. To convert values reported from GI/L (= $10^{9}/L$) to count per uL (= cells/mm³), multiply the value by 10^{3} or 1000.

Example: (0.25 GI/L) x (1000) = 250/uL

Rare B-cell subsets are reported in counts per milliliter (mL). Rare B-cell subsets reported in GI/L will be converted to cells/ml using the following formula:

Normalized count/mL = (rare cell events) / (CD19+ events) * (CD19+ count/uL) * 1000

Note, the total B-cell (CD19+) concentration from the TBNK panel should be converted to count/uL prior to the normalization and conversion of the Rare B-cell subset.

Example: Normalization and conversion of Plasma CD20-CD138+ to count/mL

Given:

- Plasma CD20-CD138+ number of events = 16
- CD19+ number of events on Plasma panel = 10250
- CD19+ concentration on TBNK panel = 0.35 GI/L

Then:

Plasma CD20-CD138+ Normalized (count/mL) = 16 / 10250 * (0.35*1000) * 1000 = 546.34 count/mL

Reporting B cell subsets

The table below includes variables, labels and details of derivations used in the reporting of the B-cell subsets for this study.

	Lab Test Code	Derivation for Normalization and / or Conversion
B-cell subset label for displays	(LBTESTCD)	of B-cell Subsets
Common B-cells		
CD19 (/uL)	CD19	May require conversion to /uL
CD20 (/uL)	CD20	May require conversion to /uL
Naive CD19+CD20+CD27- (/uL)	CDX136	May require conversion to /uL
Naive CD19+CD20+CD27- (%CD19)	CDX13619	N/A
Memory CD19+CD20+CD27+ (/uL)	CDX137	May require conversion to /uL
Memory CD19+CD20+CD27+ (%CD19)	CDX13719	N/A
Rare B-cells		
Activated CD19+CD20+CD69+	CDX141N	CDX155 EVENTS, CD19 EVENTS from Plasma
Normalized (COUNT/mL)		Panel and CD19 concentration from TBNK Panel

2018N381035_00

BEL116027

Plasma CD19+CD20-CD138+	CDX143N	CDX143 EVENTS, CD19 EVENTS from Plasma
Normalized (COUNT/mL)		Panel and CD19 concentration from TBNK Panel
Plasmacytoid CD19+CD20+CD138+	CDX145N	CDX145 EVENTS, CD19 EVENTS from Plasma
Normalized (COUNT/mL)		Panel and CD19 concentration from TBNK Panel
SLE Subset CD19+CD38b+CD27b+Lymph	CDX156N	CDX156 EVENTS, CD19 EVENTS from Plasma
Normalized (COUNT/mL)		Panel and CD19 concentration from TBNK Panel

13.7. Appendix 7: Reporting Standards for Missing Data

13.7.1. Premature Withdrawals

Element	Reporting Detail
General	Subject study completion (i.e. as specified in the protocol) was defined as s
	• Treatment holiday group: completion of the 24-week treatment holiday period plus the belimumab re-introduction treatment period to Week 52.
	• Control and long-term discontinuation groups: completion of all visits to Week 52.
	For reporting purposes, withdrawal from the maintenance phase is defined in Section 13.6.2.
	Withdrawn subjects were not replaced in the study
	All available data from participants who were withdrawn from the study will be listed and all available planned data will be included in summary tables and figures, unless otherwise specified.
	Withdrawal visits will be slotted as per Appendix 3: Assessment Windows or will be summarised as withdrawal visits.

13.7.2. Handling of Missing Data

Element	Reporting Detail
General	 Missing data occurs when any requested data is not provided, leading to blank fields on the collection instrument: These data will be indicated by the use of a "blank" in subject listing displays. Unless all data for a specific visit are missing in which case the data is excluded from the table. Answers such as "Not applicable" and "Not evaluable" are not considered to be missing data and should be displayed as such.
Outliers	• Any participants excluded from the summaries and/or statistical analyses will be documented along with the reason for exclusion in the clinical study report.
LOCF	 In the LOCF dataset, missing values will be carried forward from the previous, non-missing available on-treatment assessment. For the TH group, LOCF will not be applied across the TH and RS phases.
SLICC/ACR Damage Index	 Missing data due to prohibited medication or study withdrawal will be imputed using LOCF For the TH group, LOCF will not be applied across the TH and RS phases.
SELENA SLEDAI,	 Missing data will be imputed using LOCF. For the TH group, LOCF will not be applied across the TH and RS phases.

Element	Reporting Detail
Rebound, PGA	 If an individual SELENA SLEDAI item data is missing at the first timepoint in the RS phase, the item will be considered not present.
Reduction in Daily Prednisone Dose	 The Dropout (DO)/Prohibited Medication (PM)=Non-responder (NR) imputation will be applied. If a subject withdraws from the study and/or receives a protocol-prohibited medication prior to a scheduled visit, the subject will be considered a non-responder (i.e. no reduction in prednisone) for that and subsequent visits.
Average daily prednisone dose	Observed data will be used with no imputation.
Auto-antibodies, immunoglobulins, biomarkers, BLyS protein	Observed data will be used with no imputation
Immunogenicity	Observed data will be used with no imputation.

13.7.2.1. Handling of Missing and Partial Dates

Element	Reporting Detail				
General	Partial dates will be displayed as captured in subject listing displays.				
Adverse Events	 The eCRF allows for the possibility of partial dates (i.e., only month and year) to be recorded for AE start and end dates; that is, the day of the month may be missing. In such a case, the following conventions will be applied for calculating the time to onset and the duration of the event: Missing Start Day: First of the month will be used unless this is before the start date of study treatment; in this case the Day 0 visit date (LTD and TH arms) or the study treatment start date (TC arm) will be used and hence the event is considered On-treatment as per Appendix 4: Study Phases and Treatment Emergent Adverse Events. Missing Stop Day: Last day of the month will be used, unless this is after the stop date of study treatment; in this case the study treatment stop date will be used. 				
	• Completely missing start or end dates will remain missing, with no imputation applied. Consequently, time to onset and duration of such events will be missing.				
Concomitant Medications and Medical History	• Medications with partial or missing start and/or stop dates will be assumed to be concomitant unless there is evidence through comparison of partial dates to suggest otherwise, for example if the day is missing, then the month and year will be compared to the month and year of the first dose date of study treatment and if the month and year are the same or later, then the medication will be considered concomitant.				

Element	Reporting Detail
Time to SFI	Evaluated up to Week 52
Flares	 If a subject takes a prohibited medication during the time period being analyzed, the subject will be considered as having a SFI flare at the start date of the prohibited medication.
	 If a subject withdraws from the study, the will be censored at last flare assessment date
	 If a subject dies, censor at the date of death
Time to Renal	Evaluated up to Week 52
Flare	• If a subject withdraws from the study, the will be censored at last renal flare assessment date
	If a subject dies, censor at the date of death
Number of SFI Flares	• If a subject withdraws from the study, dies or takes a prohibited medication, the subject will be considered as having a SFI flare.
Number of days of daily prednisone dose ≥7.5 mg/day and/or increased by 25%	 The Dropout (DO)/Prohibited Medication (PM)=Non-responder (NR) imputation will be applied. If a subject withdraws from the study and/or receives a protocol-prohibited medication, the subject will be considered to have met this endpoint criteria (i.e, dose ≥ 7.5 mg/day and/or increased by 25%) after the date of dropout or the date that the medication is started, whichever comes first, up until the visit date, and for those days in intervals for subsequent attended visits. Before this date, the evaluated endpoint will be assessed using available data.
Number of days of daily prednisone dose ≤7.5 mg/day and/or decreased by 25%	 The Dropout (DO)/Prohibited Medication (PM)=Non-responder (NR) imputation will be applied. If a subject withdraws from the study and/or receives a protocol-prohibited medication, the subject will be considered a non-responder for this endpoint criteria (i.e., dose >7.5 mg/day and/or did not decreased by 25%) after the date of dropout or the date that the medication is started, whichever comes first, and for those days in intervals for subsequent attended visits. Before this date, the evaluated endpoint will be assessed using available data.
Reduction in Daily Prednisone Dose	 The Dropout (DO)/Prohibited Medication (PM)=Non-responder (NR) imputation will be applied. If a subject withdraws from the study and/or receives a protocol-prohibited medication prior to a scheduled visit, the subject will be considered a non-responder (i.e. no reduction in prednisone) for that and subsequent visits.

